Prevalence of AD Use during Pregnancy. As previously demonstrated, based on data derived from health insurance and hospital records, investigators found that ADs were prescribed to nearly 8% of all pregnant women(2). The investigators found that AD use during pregnancy increased from 2.0% of all deliveries in 1996 to 7.6% of all deliveries in 2004 and 2005, with consistently more women dispensed an AD during the first trimester of pregnancy than in either the second or the third trimester. Clinicians must weigh the morbidity associated with depressive relapse and recurrence in the mother against the risk of adverse birth outcomes that may be associated with medication exposure for the fetus. In order to avoid fetal exposure to ADs where attendant risks of in utero exposure is incompletely delineated, many women discontinue these medicines regardless of risk for recurrence.

High Risk of Relapse of Depression during Pregnancy among Women who Discontinue Maintenance AD Therapy. Studies conducted over the last decade have demonstrated that prevalence of depression during pregnancy is similar to age-matched non-pregnant women, replacing previously held ideas that pregnancy was protective against psychiatric illness. Left untreated, depression can negatively impact both the mother and the fetus. For women with histories of MDD who discontinue AD medication to avoid fetal drug exposure, the risk of depressive relapse is high. In a multi-site NIMH funded collaborative study, the rate of depressive relapse among women with a history of MDD who discontinued ADs (68%) was significantly higher than the rate (26%) for women who maintained AD treatment(3). In this study, continued AD treatment during pregnancy significantly reduced the risk of maternal depressive relapse. Data from this large scale, multi-site study also demonstrated that there is a broad distribution of AD use early in pregnancy that is not wholly determined by severity of illness as defined by number of episodes of MDD. In fact, there was no association between the decision to discontinue medication during pregnancy and duration of illness, number of previous episodes, or frequency of co-morbid psychiatric illness.

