### **Treatment Decisions during Pregnancy Are Not Driven by Illness Severity**

In a naturalistic prospective study, investigators found that over 43% of women discontinuing AD medications due to pregnancy concerns relapsed, over 50% during the first trimester(3). It could be expected that without random assignment to participation in the study, the participants who elected to enroll would be those with the least severe depression histories. This presumes patients with a history of multiple episodes would disproportionately choose to continue pharmacologic treatment, as compared to women with histories of fewer or more mild illness. However, data from a large scale, multi-site study conducted Cohen, et al. show that there is a broad distribution of AD use early in pregnancy in patients that is not wholly confounded with severity of illness as defined by number of episodes of major depression. We found no association between the decision to discontinue medication during pregnancy and duration of illness, number of previous episodes, or frequency of co-morbid psychiatric illness(3).

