## **II. SPECIFIC AIMS**

### **a. Specify objectives and hypotheses to be tested**

**Objective:** The overarching goal of this investigation is to assess EnBrace as a treatment for the acute treatment and prevention of depression in women with a history of major depressive disorder who decide to avoid or discontinue their maintenance AD treatment for pregnancy. After completing this protocol, we plan to use the preliminary data for the development of a randomized controlled trial protocol. We will include two groups of women who are interested in minimizing medication exposures while trying to conceive or during pregnancy: 1) women who have histories of depression and are not depressed, and would like to stop antidepressants for pregnancy, 2) women in depressive episodes who are pregnant or trying to conceive (on or off of antidepressant medications).

**Specific Aim 1a:** To evaluate the efficacy of EnBrace when used as maintenance treatment for MDD in a group of women (N=10) who are trying to conceive or are early in pregnancy and who

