## Partners Human Research Committee Detailed Protocol

have decided to stop ADs (Group 1). Relapse rates for women in this context have been demonstrated to be high, with 68% relapse rates in a large multisite NIMH-funded trial.

**Specific Aim 1b:** To evaluate the efficacy of EnBrace when used as an acute treatment for MDD in a group of women (N=10) who are trying to conceive or are early in pregnancy (Group 2). Women will have major depressive episodes in this group, and may receive EnBrace as monotherapy, or as an adjunct to current pharmacotherapy.

*Hypothesis 1a:* We hypothesize that relapse rates will be lower for women who receive EnBrace compared to historical controls. MDD relapse will be determined by the Mini-International Neuropsychiatric Interview (MINI) mood module that will be administered by a study clinician at each visit.

*Hypothesis 1b:* We hypothesize that the majority of women who receive EnBrace will experience a response (50% improvement in depressive symptoms) to EnBrace therapy.

**Specific Aim 2:** To identify biological markers as potential predictors of response to EnBrace.

*Hypothesis 2:* We hypothesize that pre- to post-treatment changes in homocysteine, folate, B12, IL-6 and CRP will be associated with response to EnBrace. We hypothesize specifically that levels of folate and B12 will increase and homocysteine will decrease temporally with treatment and be predictive of prevention of depressive episodes. We hypothesize that treatment will lower IL-6 and CRP levels due to the anti-inflammatory components of EnBrace (i.e., omega-3 fatty acids) and that decreased levels of inflammatory markers may predict lower risk of depressive relapse in participants who enter the study while not on a depressive episode (Group 1), and will predict response to treatment in women who enter the study while in a depressive episode (Group 2).

**Specific Aim 3 (Exploratory):** To identify factors influencing adherence to and tolerability of treatment. This will be achieved by using qualitative methods to explore (a) perceived risks and benefits of treatment; (b) perceived side effect profile; (c) treatment convenience; (d) knowledge of, attitudes towards, and preferences for depression treatment while attempting to conceive or early pregnancy.

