**Schedule of Assessments: Acute Phase (12 weeks)**

Visit #	V1	V2	V3	V4	V5	V6	V7
Week #	0	2	4	6	8	10	12
MINI: full MINI at V1; depression module at follow-ups	X	X	X	X	X	X	X
Demographics, medical & psychiatric history	X						
Labs: genetic sample	X						
Labs: folate, homocysteine, B12, IL-6, CRP	X			X			X
Vital Signs: Height only at V1, weight, blood pressure	X	X	X	X	X	X	X
MADRS	X	X	X	X	X	X	X
CGI-Clinician	X	X	X	X	X	X	X
EPDS	X	X	X	X	X	X	X
QIDS-SR	X	X	X	X	X	X	X
Q-LES-Q-SF	X			X			X

A Qualitative interview will be conducted by study staff after completion of the acute treatment phase in order to obtain feedback on the intervention.

Instrument Descriptions:

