## V. BIOSTATISTICAL ANALYSIS

We will compare the rates of depressive relapse and duration of time out of a depressive episode for Group 1 participants, and compare these data to historical controls that were also assessed prospectively. For Group 2, we will compare depressive response rates (response defined as 50% reduction in depressive symptoms on the MADRS, our primary outcome) to response rates in studies of SSRIs for the treatment of depression.

In addition, we will monitor depressive symptom burden with continuous variables across the treatment study for both groups.

To control for prenatal vitamin (PNV) use, we will supply a standard PNV to each participant to take daily in combination with EnBrace. The Sponsor has offered to supply the PNV, such that each participant will take the same PNV; this will lower the risk of inconsistencies between participants. In the statistical analysis, the data collected in this preliminary study will be compared to historical controls with a history of MDD who discontinued AD maintenance therapy during pregnancy, most of which were taking standard PNVs, but not EnBrace. This reference will allow us to estimate the relative efficacy of EnBrace in relapse prevention of women who discontinue maintenance ADs for pregnancy.

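### Hypothesis 1a compares ten women's relapse rate with historical controls without an interval or a criterion for concluding that it is lower; read literally against 68%, an unchanged true rate would look lower 40% of the time

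*Combined protocol and SAP*

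**What the plan says.** Specific Aim 1a is an efficacy aim: "To evaluate the efficacy of EnBrace when used as maintenance treatment for MDD in a group of women (N=10"). The reference rate follows directly: "Relapse rates for women in this context have been demonstrated to be high, with 68% relapse rates in a large multisite NIMH-funded trial". Hypothesis 1a then gives a direction and nothing more: "We hypothesize that relapse rates will be lower for women who receive EnBrace compared to historical controls".

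Section V (Biostatistical Analysis) sets out the Group 1 analysis: "We will compare the rates of depressive relapse and duration of time out of a depressive episode for Group 1 participants", to be set against prospectively assessed historical controls. It adds the inference to be drawn: "This reference will allow us to estimate the relative efficacy of EnBrace in relapse prevention of women who discontinue maintenance ADs for pregnancy". Neither Section II nor Section V names a test, a confidence interval, an error rate, a count of relapses that would count as lower, or a basis for the sample size. The number of women behind the historical rate is not given.

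Follow-up is fixed by the visit table, "Schedule of Assessments: Acute Phase (12 weeks"). The objective in Section II describes the study as a source of preliminary data for a later randomised trial.

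**The concern.** In ten women the observed relapse rate moves in steps of 10 percentage points, and its sampling error is large. Being numerically below a fixed figure is then weak evidence. With no interval required and no criterion written down, a result of 4, 5 or 6 relapses could be reported as agreeing with Hypothesis 1a, and as an estimate of relative efficacy, although it is compatible with no effect. It could then be carried into the design of the randomised trial. An undefined criterion also allows the standard for a lower rate to be settled after the data are seen.

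**Working it through.** The plan states no power, error rate or threshold, so there is no figure of its own to reproduce. The check uses the exact binomial distribution.

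**Inputs**
- n = 10 in Group 1 (Specific Aim 1a; Recruitment Sources).
- Benchmark 68% (Specific Aim 1a). The Section I subsection on relapse after stopping maintenance treatment gives the same figure with its comparator: "the rate of depressive relapse among women with a history of MDD who discontinued ADs (68%) was significantly higher than the rate (26"%) under maintained treatment.
- Under the same citation, the Section I subsection on treatment decisions gives another rate: "over 43% of women discontinuing AD medications due to pregnancy concerns relapsed".
- Average relapse on placebo of 41% in a meta-analysis (Section I, Depression is a Recurrent Illness).
- Follow-up of 12 weeks (Schedule of Assessments).

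**Step 1. The literal reading.** 6/10 = 60% is below 68% and 7/10 = 70% is above it, so lower means 6 or fewer relapses. With X ~ Binomial(10, 0.68), P(X ≤ 6) = 0.4044. Since P(X ≤ 3) = 0.0155, counts of 4, 5 or 6 supply 0.4044 − 0.0155 = 0.3889 of that.

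**Step 2. What those counts can exclude.** Exact (Clopper-Pearson) 95% intervals for n = 10:

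| Relapses | 95% interval | Excludes 68%? |
|---|---|---|
| 3 | 6.7% to 65.2% | yes |
| 4 | 12.2% to 73.8% | no |
| 5 | 18.7% to 81.3% | no |
| 6 | 26.2% to 87.8% | no |

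**Step 3. The time window.** The documents do not say over what period the 68% accrued. Assume, for illustration, a constant hazard and an accrual period of W weeks. The 12-week rate with no effect is then 1 − 0.32^(12/W).
- W = 26: 1 − 0.32^(12/26) = 41%, and P(X ≤ 6) = 94%.
- W = 40: 1 − 0.32^(12/40) = 29%, and P(X ≤ 6) = 99%.

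If the true rate without effect were the 43% in Section I and the benchmark stayed at 68%, P(X ≤ 6) = 91.9%. If 43% were itself the benchmark, lower would mean 4 or fewer, and P(X ≤ 4 | 0.43) = 55.6%.

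**Step 4. An interval rule, and what it depends on.** Conclude a lower rate only if the upper exact 95% limit is below the benchmark.
- Benchmark 68%, 10 evaluable: 3 or fewer relapses. One-sided error at a true 68% is 0.0155. The chance of meeting the rule is 75.2% at a true 26% and 17.2% at 50%.
- Benchmark 68%, 9 evaluable: the upper limit is 70.1% for 3/9 and 60.0% for 2/9, so 2 or fewer are needed.
- Benchmark 43%, 10 evaluable: the upper limit is 44.5% for 1/10 and 30.8% for 0/10, so only zero relapses qualify. At a true 26% that has probability 0.74^10 = 4.9%.
- Cut-off left at 3 of 10 when the true rate without effect is below 68%: P(X ≤ 3) is 31% at 43%, 36% at 41% and 68% at 29%. These would be false conclusions of benefit.

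**The case against.** The strongest reply is that Hypothesis 1a is a directional expectation and not a success rule. This stands in part. A reader might infer that the plan itself declares success at any rate below 68%, but the documents do not say so. They leave the criterion undefined, and the 40.4% belongs to the literal reading. The defect is the missing criterion and interval.

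A second reply is that this is a 20-woman preliminary study. A reader might infer that the decision to run the randomised trial turns on this one comparison. The documents set no such gate, and Section V also plans time out of a depressive episode and continuous symptom measures. That limits the consequence. It does not remove it, because Aim 1a and Section V use the language of efficacy.

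A third reply concerns the remedy. A reader might infer from Step 4 that 3 or fewer of 10 is a safe cut-off with a 1.6% false-positive chance. The documents do not support that as a fixed rule. It needs a 68% relapse rate within 12 weeks in the absence of effect, a benchmark known without error, and ten evaluable women. The accrual period and the historical denominator are not stated, and the Drop criteria allow early exits, including Group 1 women who restart treatment while well. This objection stands, so any cut-off has to be conditional.

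The 95% level is also a choice. Accepting 4 or fewer of 10 would carry a one-sided error of 6.4% and a 91% chance of being met at a true 26%. Whichever level is preferred, it should be written down beforehand.

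**Conclusion.** The point holds as a missing interval and a missing criterion attached to an efficacy claim. Against 68%, with ten evaluable women and the benchmark treated as exact, a true rate of 68% would give an observed rate below the benchmark 40.4% of the time, almost all of it from counts whose exact intervals still include 68%. If the 68% accrued over more than 12 weeks, the chance is higher: 94% to 99% under the assumed constant hazard over 26 to 40 weeks. Losing women does not reliably reduce it. At a true 68% the chance of a rate below 68% is 58.9% with nine evaluable, 49.9% with eight and 39.9% with seven. The preliminary purpose of the study makes this a matter to correct in the text and does not call the design into question.

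**What to change.** In Section V, with matching wording in Hypothesis 1a:

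1. Report the Group 1 relapse proportion with its Clopper-Pearson 95% interval, whatever the result. Define the evaluable women who form the denominator, including how early exits under the Drop criteria are counted.
2. State, before data are seen, a benchmark matched to the 12-week follow-up and its source. Conclude that the rate is lower than historical only if the upper limit is below that benchmark; otherwise call the result inconclusive.
3. Replace the relative-efficacy sentence with one saying that the relapse rate, with its interval, will be described beside the historical rate.

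The required count should be derived from the benchmark and the evaluable number, not printed as a constant. As illustration only, it is 3 or fewer of 10 against 68%, 2 or fewer of 9 against 68%, and 0 of 10 against 43%. A benchmark as low as 43% would in practice leave this group able only to describe, and the plan should then say so.

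The cost is a few sentences and the work of finding a 12-week historical rate. The downside is that a favourable-looking 4 to 6 relapses in ten could no longer be claimed as support.

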### **Selection of Intervention (EnBrace prenatal supplement)**

The current study will provide evidence regarding the efficacy, tolerability, feasibility and acceptability of a selected non-psychotropic treatment alternative to AD use while women are trying to conceive or during pregnancy. We hypothesize that rates of MDD relapse coinciding with AD discontinuation proximate to pregnancy may be attenuated if there are other effective treatments available to women.

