*Hypothesis 3:* We hypothesize that EnBrace will be perceived by patients as 1) an acceptable and attractive treatment with a favorable risk/benefit profile in the context of pregnancy or while trying to conceive, 2) well tolerated, 3) convenient and easy to adhere to, 4) will be a treatment that women who are trying to conceive or who are pregnant find intuitive and preferable to prescription antidepressant medication (or for women on antidepressant treatment in Group 2, who prefer the augmentation with EnBrace rather than an increase in antidepressant dose or augmentation with a prescription psychotropic medication).

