### Drop criteria:

## Partners Human Research Committee Detailed Protocol

1. Participant experiences severe worsening of depression symptoms, as indicated by a CGI-I of 6 or 7 on 2 consecutive visits determined by a licensed study psychiatrist. Subjects with a CGI-I of 6 or 7 on 2 consecutive visits will be terminated from the study and referred for additional clinical treatment as needed.
2. A Group 1 participant who is not experiencing depression symptoms decides to restart antidepressant treatment while they are well
3. A Group 2 participant who enrolled during a current depressive episode has either started a new antidepressant or increased the dose of an antidepressant they were already taking
4. Emergence of suicidal ideation, homicidal ideation, or psychotic symptoms. The anchors for suicidality will include the QIDS-SR, Question 12 (with an answer of 2 or 3) and the MADRS, Question 10 (with an answer of 4, 5, or 6). Acute suicidality, based on these measures and the licensed psychiatrist's clinical assessment, will result in termination of participation in the study and swift triage to the Acute Psychiatry Service at Massachusetts General Hospital.
5. Evidence of abuse or misuse of study medication
6. Evidence of current alcohol and/or drug abuse
7. Any severe or unstable medical illness that includes concern regarding safety of continued use of study medication
8. Intolerance to study medication as determined by research clinician
9. Significant hypersensitivity reaction
10. Inability or unwillingness to complete the study procedures

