## **VIII. MONITORING AND QUALITY ASSURANCE**

During the course of the protocol, study and non-study related events such as hospitalization or recurrence of depression may occur, therefore risk management protocols are in place to address these events as they occur. All professional and technical staff are fully trained and available to manage adverse events. Physicians are available by phone and pager to be informed of serious adverse events. These events will be promptly reported to the MGH IRB, according to the Code of Federal Regulations, and the subject's primary care and mental health providers will also be informed.

At each visit, study physicians will prompt the participant to report any occurrences of health problems beyond the subject's depression. Any serious or non-serious adverse event will be recorded in the participant's study binder at each examination. Serious and non-serious adverse events will also be reported to the Human Research Committee in accordance with Human Research Committee reporting guidelines, following the timeframes specified by the Partners Investigator's Guidelines. In case of a serious adverse event, appropriate diagnostic and therapeutic measures will be taken, as determined by the investigator. All adverse event reports will be reviewed by the principal investigator and reported to the FDA in accordance with the guidelines outlined in the Investigational New Drug application.

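### The plan promises evidence on tolerability, but its only stated method is a post-treatment interview, and Section V plans no summary of adverse events or intolerance removals

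*Combined protocol and SAP*

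**What the plan says.** In the Background, under Selection of Intervention, the protocol states: "The current study will provide evidence regarding the efficacy, tolerability, feasibility and acceptability" of the chosen treatment. Tolerability stands there in its own right and is not limited to what patients perceive.

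Specific Aim 3, labelled exploratory, is the only aim that takes it up: "To identify factors influencing adherence to and tolerability of treatment". Its method follows: "This will be achieved by using qualitative methods to explore" four topics, one of which is side effects as the woman perceives them. Hypothesis 3 opens "We hypothesize that EnBrace will be perceived by patients as" and lists good tolerability among the expected perceptions. No criterion or threshold is attached.

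The note under the Schedule of Assessments describes one qualitative interview, held when the 12-week acute phase has been completed. No interview is described for women who leave early.

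The Drop criteria include item 8, "Intolerance to study medication as determined by research clinician", and item 9, a significant hypersensitivity reaction.

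Section VIII has physicians ask about health problems at each visit: "Any serious or non-serious adverse event will be recorded in the" study binder. The stated uses are review by the principal investigator and reporting to the Human Research Committee and the FDA.

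Section V begins "We will compare the rates of depressive relapse and duration of time out of a depressive episode" and goes on to MADRS response, continuous symptom burden and, as exploratory work, laboratory biomarkers. It does not mention adverse events, withdrawals, tolerability or Aim 3.

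**The concern.** A woman who cannot tolerate the product is taken out of the study. If the tolerability conclusion then comes from interviews held at the end of treatment, the women with the worst experience are the ones least likely to contribute. The result would describe perceptions among those who stayed, yet it could be read as a statement about everyone treated.

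The records that would correct this largely exist, since adverse events are recorded at each visit and intolerance is a formal ground for removal. The analysis section has no step that brings them into the results. The data are meant to help design a randomized trial (Section II, Objective), and Section VI itself raises the possibility of intake above recommended levels when EnBrace is combined with a prenatal vitamin. A tolerability statement carried forward from this pilot should have a count over all treated women behind it.

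**Working it through.** The plan states no figure for tolerability: no expected rate, threshold or dropout allowance. There is therefore nothing to reproduce, and the check is mainly a comparison of sections.

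**Step 1. What is promised, and what delivers it**

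| Element | Where | Covers all treated women? | Used in Section V? |
|---|---|---|---|
| Evidence on tolerability | Background, Selection of Intervention | Not limited to perception | No |
| Qualitative interview (Aim 3) | Section II; note under Schedule of Assessments | Probably not: held after the acute phase is completed | No |
| Adverse events | Section VIII | Yes, at each visit attended | No |
| Removal for intolerance or hypersensitivity | Drop criteria, items 8 and 9 | Yes, as a status; recording of the reason is implied, not stated | No |

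The one source tied to the tolerability aim is the one least likely to include women who left because of the product. The two sources that do include them have no planned summary.

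**Step 2. What a count over all treated women could show**

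Inputs: 10 women planned per group, 20 in total (Section III, Recruitment Sources).

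With zero events among n women, the exact (Clopper-Pearson) two-sided 95% upper limit is 1 − 0.025^(1/n).

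- n = 20: 1 − 0.025^(1/20) = 1 − 0.832 = 16.8%.
- n = 10: 1 − 0.025^(1/10) = 1 − 0.692 = 30.8%.

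Even a clean record could not exclude an intolerance rate of about one in six overall, or about three in ten within a group.

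With k removals among 20, where k is assumed because the documents give no rate:

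| k of 20 | Estimate | Exact 95% interval |
|---|---|---|
| 1 | 5.0% | 0.1–24.9% |
| 2 | 10.0% | 1.2–31.7% |
| 3 | 15.0% | 3.2–37.9% |
| 4 | 20.0% | 5.7–43.7% |

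**Step 3. Whether any such removal is likely in a study of this size**

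The chance of at least one among 20 women is 1 − (1 − p)^20, with p the assumed true rate.

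- p = 5%: 1 − 0.95^20 = 64%.
- p = 10%: 1 − 0.90^20 = 88%.
- p = 20%: 1 − 0.80^20 = 99%.

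Across this assumed range, at least one woman would more likely than not leave for intolerance, so whether she is counted matters even with 20 women.

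**The case against.** The strongest reply is that Aim 3 does what it sets out to do. It is exploratory, it looks for factors that influence tolerability, and Hypothesis 3 is worded in terms of perception. Interviews are a proper tool for that. This stands: a reader might infer that the qualitative method is wrong for Hypothesis 3, and the documents do not support that reading. What remains is the gap between perceived tolerability and the tolerability evidence that the Background promises.

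A reader might also infer that adverse events will be excluded from the results or go unreported. The documents do not say so. Section V is silent, and Section VIII sends the events to the principal investigator, the Human Research Committee and the FDA. What is missing is a planned summary.

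A further tempting reading is that the interview is restricted to completers. That is inferred from its timing. The protocol does not bar women who stop early; it only describes no interview for them. The inference is reasonable but remains an inference.

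It might also be argued that removals for worsening depression or suicidality (Drop criteria, items 1 and 4) would vanish from any safety account because the visit prompt concerns problems other than depression. That goes too far. Section VIII names recurrence of depression and hospitalization among the events to be managed, and mood is rated at every visit. Worsening depression is also an efficacy matter, not intolerance.

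Lastly, the withdrawal counts above are assumptions, and an interview does not yield a proportion that could be set against them. They indicate scale and do not estimate a bias. By-group intervals will be wide. These objections lower the severity; none supplies the missing summary.

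**Conclusion.** The point holds as a gap between a stated purpose and the planned analysis. If the plan is followed as written, any tolerability conclusion would come from interviews that probably leave out the women removed for intolerance or hypersensitivity, with no planned count over all treated women beside it. The interview can support statements about perceived tolerability and acceptability among those interviewed. It cannot alone support the statement that EnBrace is well tolerated.

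The size of any distortion cannot be calculated, because the documents give no rate. The firm figure is the precision available: no events among 20 women is compatible with a true rate of up to 16.8%. The conclusion rests on two assumptions: that the interview is in practice held only with women who reach the end of the acute phase, and that no adverse event or withdrawal summary is planned beyond what Section V states.

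Severity is minor to moderate. The aim is exploratory, the study is an uncontrolled 20-woman pilot, and no efficacy aim depends on this result.

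**What to change.** Add to Section V, with a cross-reference from Aim 3:

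- For every woman who took at least one dose, overall and by group, report the number with any adverse event, the number with any serious adverse event, and the number removed under Drop criteria items 8 or 9, each with an exact 95% interval. Count women, not events.
- Record the reason for each withdrawal. The Drop criteria imply this but do not state it.
- List removals under items 1 and 4 separately, as disposition and not as intolerance.
- State how many women were interviewed out of all treated, and limit interview-based conclusions to perceived tolerability and acceptability among those women.

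The interview itself stays as planned. The cost is one extra table, a few sentences in Section V and a reason-for-withdrawal entry for each woman who leaves. No visit, assessment or clinical rule changes. The only downside is that the resulting statement may be less favourable.
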